### 7.2 Interventions:

Study medication, to include 10-mg suvorexant and matching placebo, will be provided by Merck. The active medication will be suvorexant 10 mg every bedtime. The research pharmacist at EvergreenHealth will randomize the subject and the subject is provided active and placebo, in separate containers labeled for proper order of consumption based on study assignment. Study medication will be dispensed at randomization (Visit 2, start of Treatment Period 1) with separate pill bottles marked "Period 1, use this bottle first" and "Period 2, use this bottle after the break." An extra 6-day supply of medication will be provided for each study period to allow a window for scheduling of appointments.

Optional Drug Titration: There will be an optional titration to two pills at night (changes to suvorexant 20mg or matching placebo) after 5-7 days of each active treatment period. This will be based on a phone interview entailing answering questions about drug tolerance and whether the participant would like to escalate the dose of drug.

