Physical examination will be performed, both a general medical examination including vital signs and a neurological examination. Neurological exam will include disability rating by expanded disability status scale (EDSS) (Kurtzke 1983). Laboratory testing will include complete blood count (CBC), complete metabolic panel (CMP), with calculation of the Child-Pugh score for any subjects with liver dysfunction. Pre-menopausal women without surgical sterilization will have urine human chorionic gonadotropin (hCG) measured.

The wearable activity/sleep monitor will be dispensed at this visit to all subjects who meet eligibility criteria. This will be a FitBit™ device worn by the subjects throughout the remainder of the study. The research coordinator will oversee patient education around FitBit use. The FitBit is easy for subjects to put on and requires minimal user programming to upload data. Recorded outcomes are described below (see outcome measures). Subjects will be encouraged to wear the monitor 24-hours per day. Patients will be instructed to complete a sleep diary for seven days prior to next visit (see 11. Outcome measures).

## 10.3 Baseline Clinic Visit 2

Clinic Visit 2 will occur within 7-14 days after the screening visit. In addition to screening for eligibility, medications will be reviewed again to ensure stability of the MS medication regimen and absence of any prohibited medications.

Following confirmation of eligibility, an eligible patient will complete the baseline assessments of the insomnia severity index (ISI), modified fatigue impact scale (MFIS), Fatigue visual analogue scale (VAS-F), Global impression. The following measures will be provided for the participants to take home for use at the time of Phone Visit 2 and Phone Visit 5: Study scales (ISI, MFIS, VAS-F, BDI, Global impression). Sleep diaries will be provided for use after Phone Visit 1 and Phone Visit 3.

Following confirmation of eligibility, an eligible patient will be randomized in a 1:1 randomization scheme to receive suvorexant 10 mg qhs or placebo. Randomization will occur at the research pharmacy of EvergreenHealth using a computer-generated randomization list. The pharmacist will maintain a codebook indicating the treatment allocation of each subject. Study medication will be delivered by the research pharmacist to the research study staff from the

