### 10.5 Cross-over Phone Visit 2 (14 days post treatment)

Phone Visit 2 will occur at the completion of the first treatment period (day 14 following baseline). Medications will be reviewed again to ensure absence of any prohibited medications. Any possible adverse events (AE) will be assessed.

Study scales (ISI, MFIS, VAS-F, BDI, Global impression) will be self-administered by the participant with study staff oversight, as needed. Data from the wearable activity / sleep monitor will be collected. Completion of the 7-days sleep diary and scales (sQUAL and sFRESH) will be verified remotely.

Subjects will be instructed to take no study medication for one week, then to start taking the study medication (active or placebo) for Period 2.

### 10.6 Phone Visit 3 : Start of Treatment Period 2

Phone Visit 3 will occur 1 week after Phone Visit 2 (day 21 after baseline) and will mark the beginning of treatment period 2. Medications will be reviewed again to ensure stability of the MS medication regimen and absence of any prohibited medications. Any possible adverse events (AEs) will be assessed.

Subjects will be instructed to begin taking drug from the bottle marked "Period 2.". All subjects who received active medication in treatment period 1 will take placebo, and all subjects who received placebo in treatment period 1 will take active medication (10mg) while double blind.

## 10.7 Phone Visit 4

Phone Visit 4 will occur 5-7 days after Phone Visit 3 to review safety and tolerability through questioning about adverse events. BDI Q9 (suicidality risk) will be administered. Subjects with answer of 2 or 3 will be asked to discontinue study medication immediately and unscheduled visit or emergency referral will be arranged. Subjects with BDI Q9 score 0 or 1 who report no AEs on suvorexant 10 mg po QHS (or matched placebo) and who report a persistent sleep disturbance will be titrated to suvorexant 20 mg po QHS (or matched placebo) using a titration decision algorhythm. At this visit, subjects will be reminded to wear sleep monitors and to start recording sleep diaries.

### 10.8 Termination Phone Visit 5

Phone Visit 5 (final visit) will occur 2 weeks after Phone Visit 3 (day 35 after baseline). Medications will be reviewed again. Any possible AE will be assessed.

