## **12.** Safety Monitoring

### 12.1 Safety measures:

Laboratory testing: All subjects: CBC, CMP. As-indicated: urinary pregnancy testing Safety will be monitored by adverse event (AE) reporting, physical examination, laboratory evaluation.

Monitoring for suicidality: The BDI is being performed due to suvorexant being a central nervous system depressant, which could cause suicidal ideation and behavior. This test is performed at screening, baseline and final visit. At phone visits 2 and 5, the BDI is administered and at phone

visit 1 and 4, question 9 of the BDI is administered to ascertain suicidal thoughts or wishes. A score of 2 or 3 on BDI question 9 indicates that the patient would be at significant suicide risk. A high score on the BDI or BDI question 9 at any point would result in immediate discontinuation of the study medication and unscheduled visit or emergency room referral, as indicated.

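### The BDI at Phone Visits 2 and 5 is scheduled, but no step has staff read it on the call or review it before Period 2 starts

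*Combined protocol and SAP*

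**What the plan says.** Section 12.1 gives the reason for the BDI: the drug is a CNS depressant and might bring on suicidal thoughts or acts. It treats a 2 or 3 on item 9 as significant risk. Its rule is that "A high score on the BDI or BDI question 9 at any point would result in immediate discontinuation of the study medication", with an extra visit or emergency referral where needed. Section 8.2 separately lists an item 9 score above 1, at any time in the study, as an exclusion.

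The schedule of events and section 12.1 place item 9 alone at Phone Visits 1 and 4 and the full BDI at Phone Visits 2 and 5. Section 12.1 uses the same verb, administered, for both pairs.

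The visit sections differ between the pairs. Sections 10.4 and 10.7 have item 9 given on the call and state what to do about a 2 or 3. For Phone Visits 2 and 5, section 10.3 says that the scales, the BDI among them, "will be provided for the participants to take home for use at the time of Phone Visit 2 and Phone Visit 5". Sections 10.5 and 10.8 say that they "will be self-administered by the participant with study staff oversight, as needed". The next check named there is for other instruments: "Completion of the 7-days sleep diary and scales (sQUAL and sFRESH) will be verified remotely". Section 10.8 has subjects post their surveys and diaries after Phone Visit 5.

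On Period 2, section 7.2 says "Study medication will be dispensed at randomization (Visit 2, start of Treatment Period 1) with separate pill bottles marked" for order of use, so the subject holds both bottles from the start. Section 10.5 adds: "Subjects will be instructed to take no study medication for one week, then to start taking the study medication". Section 10.6 (Phone Visit 3) lists a medication review and adverse events, with no BDI or item 9.

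**The concern.** A rule of immediate action works only if someone on the study team learns the answer promptly. At Phone Visits 1 and 4 the visit section provides for that. At Phone Visits 2 and 5 it does not say who looks at the form, or when.

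Two things are at stake. The first is referral: a subject who marks 2 or 3 on day 14 or day 35 may not be evaluated promptly. The second is the start of Period 2. The instruction to begin the second bottle is given on the Phone Visit 2 call and repeated at Phone Visit 3, and neither is tied to the BDI result. In a placebo-first subject, suvorexant could then be started in someone who already meets the section 8.2 criterion.

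The end-of-period form also carries weight of its own. Within each period, staff ask item 9 before the titration decision on the same call, so the BDI at Phone Visit 2 or 5 is the only scheduled suicidality measure that covers the nights at the higher dose.

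**Working it through.** The plan gives no figure on this point to reproduce. The check is a comparison of the visit sections, followed by day counts.

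**Comparison of the two pairs of calls**

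| | Phone Visits 1 and 4 (10.4, 10.7) | Phone Visits 2 and 5 (10.3, 10.5, 10.8) |
|---|---|---|
| Instrument | Item 9 alone | Full BDI, including item 9 |
| How given | By staff on the call | Take-home form, self-administered, oversight as needed |
| When staff learn the answer | On the call | Not stated; the only stated return is the mailing after Phone Visit 5 |
| Action in the visit section | Stop and refer on 2 or 3 | None; only the general rules in 12.1 and 8.2 |
| Condition on the next step | Titration needs item 9 of 0 or 1 | Start of Period 2 has none |

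**Inputs for the day counts (nominal days after baseline)**

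- Phone Visit 1: day 5 to 7 (10.4)
- Phone Visit 2: day 14 (10.5)
- Phone Visit 3, start of Period 2: day 21 (10.6)
- Phone Visit 4: 5 to 7 days after Phone Visit 3 (10.7), so 21 + 5 = 26 to 21 + 7 = 28
- Phone Visit 5: day 35 (10.8)

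**If staff read the form on the call:** the delay is 0 days at both visits.

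**If staff follow the visit sections literally and do not read it:**

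- Day-14 form to the next staff-asked item 9: 26 − 14 = 12 to 28 − 14 = 14 days.
- Period 2 dosing already under way by then: 26 − 21 = 5 to 28 − 21 = 7 days.
- Placebo-first subjects, last staff-asked item 9 to the first suvorexant dose: 21 − 7 = 14 to 21 − 5 = 16 days.
- Day-35 form: no later contact is scheduled, so the delay lasts until the envelope arrives. The documents give no time for that.

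**Nights at the higher dose covered only by the end-of-period form:** for a titrated subject in the active period, 14 − 7 = 7 to 14 − 5 = 9 nights.

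With 1:1 allocation of 50 subjects, each sequence has about 25. That is the size of the sequence, not a number at risk. The documents give no rate of item 9 answers of 2 or 3, so no event probability can be stated. Section 7.2 allows a 6-day extra supply per period for scheduling, so actual intervals may differ from these.

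**The case against.** The strongest reply is that the check is planned and the rule already covers it. Section 12.1 says that the BDI is administered at Phone Visits 2 and 5, with the same verb as for item 9 at the other calls. A duty to act at once implies timely reading. The subject is remote, so a form used at the time of the visit has to be at home already, and staff oversight is mentioned. The diary needs a completion check because it is filled in over seven mornings, so leaving the BDI out of that sentence does not show that staff never see it. Study drug is paused at Phone Visit 2 and stopped at Phone Visit 5 in any case. For suvorexant-first subjects, Period 2 is placebo: "All subjects who received active medication in treatment period 1 will take placebo". Adverse events are asked about live on every call.

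Much of this stands, and it rules out three stronger readings that a reader might infer:

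- **That Period 2 starts with no suicidality check before it.** A BDI including item 9 is scheduled seven days earlier (21 − 14 = 7). What is missing is stated staff review of it.
- **That no check covers the nights at 20 mg.** This holds only if the end-of-period BDI is left out of the count.
- **That a day-14 answer stays unknown for at least 35 − 14 = 21 days, until mailing.** Section 10.8 describes the return of materials. It does not say that staff first see the answers then, and item 9 is asked again on day 26 to 28.

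What the reply does not supply is the operating step. Oversight as needed permits staff to ask for the score but does not require it. The general rules give the trigger, not the means of learning that it has been met. The adverse event questions are a partial backstop, but the text does not direct them at suicidality.

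**Conclusion.** The point holds as a gap in procedure: the BDI is scheduled and the action rule exists, but sections 10.5 and 10.8 do not have staff read the form on the call, and the start of Period 2 is not conditional on it. On a literal reading, a positive day-14 answer could go unread for 12 to 14 nominal days, with Period 2 dosing begun. In suvorexant-first subjects the harm is late referral. In placebo-first subjects it is also a start of active drug that section 8.2 is meant to prevent. At Phone Visit 5 only the referral can be late.

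These intervals are worst cases. They assume that staff do not ask for the score and that nothing emerges from the adverse event questions. If staff do read the form on the call, the delay is nil. The plan should say which applies, because both are consistent with its text. A related gap is that section 12.1 does not say which on-treatment BDI total counts as high; section 8.2 gives above 28 for screening only.

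This is a change that should be made because it is cheap and concerns safety. It does not affect the efficacy analysis.

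**What to change.** - **Sections 10.5 and 10.8:** staff obtain and record the item 9 answer and the BDI total during the call, and ask item 9 aloud if the form has not been completed. An answer of 2 or 3 triggers the section 10.4 action the same day.
- **Sections 10.5 and 10.6:** staff give the instruction to start the Period 2 bottle only after an item 9 answer of 0 or 1 has been reviewed, at the latest at Phone Visit 3.
- **Section 12.1:** state the on-treatment BDI total that counts as high, for example above 28, as at screening.

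The cost is a few minutes on two calls that already take place, with no new visit, form or test. The downside is that some subjects may answer item 9 less candidly when speaking to staff, so the written BDI should be kept as the exploratory score.

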#### **12.2 Adverse Events**

Subjects will be monitored for adverse events throughout the trial. The occurrence of adverse events will be ascertained by observation, telephone monitoring and questioning by the investigator. Safety assessments will consist of monitoring and recording all adverse events, including serious adverse events.

An AE is any symptom, physical sign, or medical condition that emerges during the study or, if present at screening, worsens during the study, regardless of the suspected cause. Adverse events include adverse drug reactions, illness with onset during the study, exacerbations of pre-existing conditions or clinically significant changes in physical examination or significantly abnormal objective test findings. Medical conditions/diseases present before starting study treatment are only considered adverse events if they worsen after starting study treatment. All adverse events will be recorded and graded as mild, moderate or severe by the principal investigator in accordance with general guidelines of clinical research, outlined here:

- MILD: An event that causes transient or minimal symptoms and that does not interfere with daily activities.
- MODERATE: An event that causes symptoms sufficient to interfere with but not prevent daily activities.
- SEVERE: An event that prevents normal, everyday activities.

Adverse events will also be classified by their relationship to the study medication by the principal investigator in accordance with general guidelines of clinical research, outlined here:

- Unrelated: There is no reasonable association between the study treatment and the suspected event and the event could have been produced by the patient's clinical state or other therapy administered to the patient.
- Possibly related: The suspected AE may or may not follow a reasonable temporal sequence from study treatment administration but seems to be the type of reaction that cannot be dismissed as unlikely. The event could have been produced or mimicked by the patient's clinical state or other therapy administered to the patient.
- Probably related: The suspected AE follows a reasonable temporal sequence from study treatment administration, abates upon discontinuation of the treatment, and cannot be reasonably explained by the known characteristics of the patient's clinical state or other treatments.

• Definitely related: The suspected AE follows a reasonable temporal sequence from study treatment administration, abates upon discontinuation of the treatment, and, if appropriate, resumes upon re-introduction of the treatment. Additionally, the suspected AE cannot be reasonably explained by the known characteristics of the patient's clinical state or other treatments.

The principal investigator and all other research staff except the research pharmacist will be blinded towards randomization of active drug versus placebo until after completion of study.

#### **12.3 Serious Adverse Events**

A serious adverse event (SAE) is any AE that meets one of more of the following criteria:

- Is fatal or life-threatening
- Requires hospitalization or prolongs a current hospitalization
- Results in persistent or significant disability/incapacity
- Is a congenital anomaly
- Requires medical or surgical intervention to prevent one of the above outcomes

If any SAE occurs, the treatment status of the subject(s) may be revealed, as clinically indicated. If a patient discontinues medication use due to an AE, the event will be followed, when possible, until resolution. No interim analysis of safety data is planned because the entire study will be conducted over 2 months. However, the frequency of AEs will be under continuous scrutiny during the trial with comparison to AE rates that have been recorded in published PD drug trials.

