Suvorexant may have other advantages that are of benefit specifically in the MS population. Suvorexant appears not to adversely affect next-day balance in healthy non-elderly subjects. In addition, suvorexant appears not to affect memory as measured by word recall. MS patients often have ataxia and cognitive impairment as a result of their disease. Orexins are considered to be involved in arousal and maintenance of the waking state. As such, suvorexant may provide unique clinical benefit as a treatment of MS fatigue with co-morbid insomnia.

This project proposes to study objective and clinical measures of insomnia, daytime sleepiness and fatigue in patients with MS fatigue and co-morbid insomnia while treated short-term with suvorexant 10-20mg versus placebo. Those qualifying will receive suvorexant and placebo for each of 14 nights in a cross over design with 7 nights of washout between treatments. There will be an optional titration to suvorexant 20mg (or matching placebo) after 5-7 days of each active treatment period. Primary outcome to be measured will be change in ISI on both conditions (Suvorexant 10/20mg versus placebo).

The primary outcome to be measured will be change from baseline for the two conditions (suvorexant 10/20 mg and placebo) on the Insomnia Severity Index.

Suvorexant is approved at doses up to 20 mg daily (Prescribing Information, Merck 2015). People with MS may be more sensitive to the therapeutic and adverse effects of suvorexant. It is also likely that subjects in a MS trial will be on other medications that may increase daytime somnolence. For these reasons, we are proposing a study of the 10-mg dose only. If suvorexant is found to be well-tolerated at a dose of 10 mg daily, future MS studies can explore the safety and efficacy of 20 mg daily.

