#### **Statistical Analysis**

Statistical analysis will be performed by a consulting statistician contracted with EvergreenHealth and whose services we have used on recent studies in MS. All data will remain blinded throughout the data analysis and will be un-blinded only in the event of a medical emergency.

Generally, the mean over the week prior to visit 2 (baseline) will be compared to the mean over the final week of Treatment Period 1 and the mean over the final week of Treatment Period 2 for treatment effects. This will be done by treatment arm. Level of significance will be p < 0.05. Minimum drug adherence for per-protocol criteria will be 75%. We plan to do both intention to treat and per-protocol analyses.

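### The only adverse-event rate comparison in the plan (section 12.3) is against published PD drug trials, an undefined comparator that is not MS, insomnia or suvorexant

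*Combined protocol and SAP*

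**What the plan says.** Section 12.3 gives this reason for having no interim look: "No interim analysis of safety data is planned because the entire study will be conducted over 2 months". It then says that AE frequency will nevertheless be "under continuous scrutiny during the trial with comparison to AE rates that have been recorded in published PD drug trials". It does not name the trials, give their rates, say whether active or placebo arms are meant, or state what difference would prompt action. PD has no entry in the abbreviation list (section 4).

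Section 12.2 covers collection: "Safety assessments will consist of monitoring and recording all adverse events, including serious adverse events". Events are graded for severity and for relationship to study drug. It also says that, besides the principal investigator, other "research staff except the research pharmacist will be blinded towards randomization of active drug versus placebo until after completion of study".

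The Statistical Analysis part of section 13 says that "the mean over the week prior to visit 2 (baseline) will be compared to the mean over the final week of Treatment Period 1", and likewise for Period 2. It does not mention AEs.

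Section 5 says of the study population: "People with MS may be more sensitive to the therapeutic and adverse effects of suvorexant". It adds: "It is also likely that subjects in a MS trial will be on other medications that may increase daytime somnolence".

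**The concern.** A check against outside rates helps only if those rates come from a similar population or the same drug. Here the comparator cannot be identified, and nothing in its wording connects it with this trial. It may have been carried over from another protocol, but that is an inference.

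The two section 5 statements are reasons to expect this trial's AE rates, on drug and on placebo, to differ from those in an unrelated population. The crossover supplies a much better control, because each subject is planned to take both treatments against the same disease and background medication. Yet no stated AE comparison uses the placebo periods.

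What is at stake is whether the scrutiny promised in 12.3 could show anything. It is offered in place of an interim safety analysis, and the reason given for omitting that analysis also looks wrong.

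**Working it through.** **1. Every place where AE rates could be compared**

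- 12.1: an individual stop rule based on the Beck Depression Inventory (BDI) and its question 9 (Q9). No comparison of rates.
- 12.2: recording, severity and causality. No comparison.
- 12.3: outside comparison with PD drug trials. This is the only one.
- 12.4: reporting of serious events to the regulator. No comparison.
- 13, Statistical Analysis: weekly means against baseline for treatment effects. The statement that this is done by arm refers to those means.

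**2. What the 12.3 comparison measures**

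Let p1 and p0 be the proportions of suvorexant and placebo periods with an AE, and r the outside rate. Staff are blinded, and each completer takes 14 nights of each treatment (14 of 28 on placebo), so they see the pooled rate (p0 + p1)/2. Then

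(p0 + p1)/2 − r = (p1 − p0)/2 + (p0 − r).

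The first term is half the drug excess. Halving is common to every blinded pooled check and is not the defect. The second term depends on how well the comparator matches this trial's placebo experience. For an unidentified comparator there is no basis for its size or even its sign. The documents give no AE rates, so I put no number on it.

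**3. The two-month reason**

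Inputs: 7–14 days from screening to baseline (10.3); final visit at day 35 after baseline (10.8); last visit in week 7–8 (Schedule of Events); N = 50 (7.1). Two months = 2 × 30.44 ≈ 61 days.

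- One subject, visit text: 7 + 35 = 42 to 14 + 35 = 49 days.
- One subject, schedule table: up to 8 × 7 = 56 days.
- Screening window if all 50 are to finish in 61 days: 61 − 49 = 12 to 61 − 42 = 19 days, or 61 − 56 = 5 days on the eight-week schedule.
- Rate needed: 50/19 = 2.6 to 50/12 = 4.2 subjects per day, or 50/5 = 10 per day on the eight-week schedule.

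Section 10.1 describes recruitment from clinical care, referrals and websites. No accrual rate is given. At assumed rates of 8, 4 or 2 subjects per month, 50/rate plus 1.4 to 1.6 months gives about 8, 14 or 26 months in total.

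**4. Precision of the trial's own comparison**

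For a paired difference near zero, the 95% half-width is about 1.96 × √(d/n), where d is the proportion of subjects with the event in only one of the two periods. The values of d are assumed:

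| d | n = 50 | n = 45 |
|---|---|---|
| 0.10 | ±8.8 points | ±9.2 points |
| 0.20 | ±12.4 points | ±13.1 points |
| 0.30 | ±15.2 points | ±16.0 points |

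These intervals are wide, but their target is suvorexant against placebo in the same subjects.

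**The case against.** The strongest reply is that 12.3 is a monitoring statement and no more. It governs scrutiny while the trial runs, when blinded staff could not compare treatments anyway. Staff stay blinded only until completion, so nothing prevents an AE table by treatment afterwards. Such tables are routine, and their absence alone would be missing detail. All of this stands.

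A reader might infer something stronger: that the final tolerability conclusion depends on which PD trials are picked. Section 5 does look ahead, with "If suvorexant is found to be well-tolerated at a dose of 10 mg daily", to later MS studies. The documents do not support that inference. Section 12.3 does not say that the end-of-trial judgement uses outside rates. The section 5 sentence sits in a paragraph proposing 10 mg only, which conflicts with the titration to 20 mg in section 7.2. The objectives in section 6 concern efficacy.

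Nor does the gap leave individual subjects unprotected. AEs are assessed at baseline and at every phone visit, the BDI and Q9 stop rule applies, treatment may be revealed after a serious event, and reporting duties are set out.

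On the two months, 12.3 says the entire study, the trial is multi-center, and no accrual period is stated that would disprove the figure. That also stands.

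What the reply does not answer is that 12.3 states an operative check whose comparator cannot be identified and has no stated link to this trial.

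**Conclusion.** The concern holds as a minor point. Followed as written, the comparison in 12.3 tells the investigators nothing reliable about suvorexant in MS, and the plan states no other AE-rate comparison. This rests on the text and on the identity in step 2, not on any assumed AE rate. The practical loss is limited to group-level monitoring during the trial and an unstated descriptive table at its end. The AE data are collected either way, and the efficacy analysis is untouched.

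The two-month point is secondary. It is a strong inference that the figure describes one subject's participation, not proof. Correcting that reason would not by itself change how the trial is run.

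**What to change.** **Section 12.3.** Replace the PD reference with named published suvorexant insomnia trials and MS trials. Write down the reference rates before enrolment, and describe the comparison as a blinded signal check only. Replace the two-month reason with the planned recruitment period plus 6 to 7 weeks per subject, and give the actual reason for no interim safety analysis.

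**Section 13.** Add text such as: AEs, serious AEs, and stops related to AEs or Q9 will be counted by the treatment taken at onset, and suvorexant will be compared with the trial's own placebo periods (paired difference in proportions with 95% confidence interval, descriptive). Washout events will be listed separately under the Period 1 treatment. Subjects who stop early stay in the counts by treatment. The table can be built under coded treatment labels, which respects the rule in section 13 that data stay blinded during analysis.

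**Cost.** A few sentences and one table from data already collected, with no new visits, tests or subjects. The stop rule in 12.1 and the eligibility criteria do not change. The downside is wide intervals at N = 50, and rare events can only be counted.
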